2.1 Primary Objective

Measure the accuracy of wearable technology for patient monitoring compared to currently used equipment in patients undergoing gastrointestinal endoscopic procedures with sedation

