3.4 Primary Safety Endpoints

There are no specific primary safety endpoints pertaining to the study given the non-invasive intervention. Wearable technology like smart watches and smart phones are already permitted within the procedural area.

4 Subject Selection, Enrollment and Withdrawal

All patients who are undergoing gastrointestinal endoscopic procedures with sedation may be eligible for the study. It is anticipated that we will screen up to 1000 subjects and enroll 500 subjects to the study.

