5.1 Sample Size Determination

Power analysis not performed as this study is descriptive and we do not plan to perform any statistical testing.

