5.2 Statistical Methods

Descriptive Statistics

Baseline values for demographic, clinical, and outcome will be tabulated for the study subjects. Continuous variables will be expressed as mean and standard deviation. Categorical variables will be expressed as percentages.

We will measure the rate of concordance between device detection and documentation in anesthesia record (# of events recorded on wearable device / events noted on anesthesia record). Events to be recorded include tachycardia (HR > 100), bradycardia (HR < 60), desaturation (peripheral O₂ saturation < 88%), any arrhythmia, and tachypnea (RR > 18).

We will also calculate the difference in maximum and minimum heart rate, respiratory rate, and oxygen saturation recorded by the watch compared to the sedation record.

Handling of Missing Data

Subjects with missing or incomplete data will be noted but will not include in the final analysis. Available information regarding these patients will be reported separately to allow for evaluation of external validity

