5.3 Subject Population(s) for Analysis

All subjects who wore the device for the duration of procedure will be included in the analysis.

6 Safety and Adverse Events

Patients will be undergoing endoscopic procedures that are clinically indicated with inherent risk of the procedure itself. There will be minimal additional risk with placement of a smart device in the pre-operative area. Wearable technologies (eg. smartphones, smart watches) are already permitted in the endoscopy suite, so this protocol would not significantly alter standard of care. Therefore, this study will not track any adverse events.

Definitions

Adverse Effect (Event)

Any untoward medical occurrence in a subject involved in clinical study of an investigational device; regardless of the causal relationship of the problem with the device or, if applicable, other study related treatment(s).

Life-threatening adverse effect: Any adverse effect that places the subject, in the view of either the investigator or the sponsor, at immediate risk of death from the effect **as it occurred**. It does not include a reaction that, had it occurred in a more severe form, might have caused death.

Serious adverse effect: An adverse effect is considered “serious” if, in the view of either the investigator or the sponsor, it results in any of the following outcomes:

- death
- a life-threatening AE
- inpatient hospitalization or prolongation of existing hospitalization
- a persistent or significant disability/incapacity
- a congenital anomaly/birth defect.

Unanticipated adverse effect: Any adverse effect, the nature, specificity, severity, or frequency of which is not consistent with the risk information in the clinical study protocol or elsewhere in the current IDE application.

All inclusion and exclusion criteria are set out and there will be no protocol deviation.

7 Data Handling and Record Keeping

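### The concordance rate in section 5.2 reads as an events-over-events ratio with no event definition, matching rule, subject weighting or interval, so if repeats count, a few subjects can dominate it

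*Combined protocol and SAP*

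**What the plan says.** The primary objective (section 2.1) is to "Measure the accuracy of wearable technology for patient monitoring compared to currently used equipment". Section 5.2 serves it with two measures.

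- **Concordance rate**, defined as "of events recorded on wearable device / events noted on anesthesia record". The events are listed, with a respiratory-rate limit of 18 closing the list: "Events to be recorded include tachycardia (HR > 100), bradycardia (HR < 60), desaturation (peripheral O₂ saturation < 88%), any arrhythmia, and tachypnea (RR >".
- **Differences in extremes**, with the sedation record as comparator: "We will also calculate the difference in maximum and minimum heart rate, respiratory rate, and oxygen saturation recorded by the watch compared to the sedation".

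For summaries, 5.2 says only "Continuous variables will be expressed as mean and standard deviation. Categorical variables will be expressed as percentages". Section 5.3 settles who is analysed ("All subjects who wore the device for the duration of procedure will be included in the analysis") but not how subjects are weighted. Section 5.1 states "Power analysis not performed as this study is descriptive and we do not plan to perform any statistical testing". The opening of section 4 expects that "we will screen up to 1000 subjects and enroll 500 subjects to the study".

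On the concordance rate, the plan does not say:

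- where an event starts and ends, or whether an event is a reading, an episode, or once per type per subject;
- whether a device event must coincide with a record event to be counted;
- whether the ratio is taken over all events together or within each subject and then averaged;
- whether it is given by event type, or separately for the wrist and torso devices described in section 3.1;
- any interval, or any allowance for events that come from the same subject.

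**The concern.** Four of the five event types are vital-sign thresholds, and a subject who hovers near a threshold can cross it repeatedly in one procedure. Each device is fitted once per subject, so a poor fit would affect all of that subject's events together. On its plain reading the ratio weights each subject by the number of events that subject has.

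Two things follow if repeats count. First, the rate can describe detection in a few subjects with many events, whereas the objective concerns monitoring of patients in general. Second, repeated events in one subject are correlated, so a rate based on several hundred events may carry the information of far fewer. A reader who judges precision from the event total would be misled.

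The missing matching rule adds to this: as written, a device event that corresponds to nothing on the record still raises the rate.

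**Working it through.** **Inputs.** From the documents: the ratio in 5.2, five event types, and 500 planned subjects. The documents give no event counts per subject, expected concordance or precision target, so there is no plan figure to reproduce. Every count, detection rate and intraclass correlation (ICC) below is an assumption.

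**1. When the two summaries differ.** Let subject i have n_i record events, with proportion p_i detected by a matched device event.

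- Pooled rate = Σ n_i p_i / Σ n_i
- Per-subject mean = average of p_i over subjects with n_i > 0
- Pooled minus per-subject mean = Cov(n_i, p_i) / mean(n_i)

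The gap is zero if all n_i are equal, or if detection is unrelated to the number of events. A gap needs both uneven counts and detection that varies with the count.

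**2. Illustration.** Assume 100 subjects have events: 95 average 1.5 each (142.5 events, 95% detected) and 5 have 30 each (150 events, 50% detected).

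- Share of events from the five = 150 / 292.5 = 51%
- Pooled = (150 × 0.50 + 142.5 × 0.95) / 292.5 = 71.9%
- Per-subject mean = (5 × 0.50 + 95 × 0.95) / 100 = 92.75%

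Changing one assumption at a time:

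| Change | Share from the five | Pooled | Per-subject mean |
|---|---|---|---|
| 10 events each in the five | 26% | 83.3% | 92.75% |
| At most 5 events per subject | 25 / 167.5 = 15% | 88.3% | 92.75% |
| 90% detected in the five | 51% | 92.4% | 94.75% |
| 95% detected in the five | 51% | 95% | 95% |

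**3. Range.** Assume 100 subjects with 1 event each (90% detected) and 10 subjects with m events each (30% detected). The per-subject mean is (90 + 10 × 0.3) / 110 = 84.5% for every m. The pooled rate is (90 + 3m) / (100 + 10m):

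| m | Pooled | Gap (points) |
|---|---|---|
| 1 | 84.5% | 0 |
| 5 | 70.0% | 14.5 |
| 10 | 60.0% | 24.5 |
| 30 | 45.0% | 39.5 |

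**4. How concentrated events could be.** In a simulation of 500 subjects averaging one event each, with gamma-Poisson counts, the 25 subjects with most events (5%) supplied 26%, 40% and 63% of events at dispersion 1.0, 0.3 and 0.1.

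**5. Precision.** Design effect for unequal clusters: DE = 1 + ((1 + CV²) × m − 1) × ICC, with m here the mean number of events per subject and CV the coefficient of variation of that number. For 500 events at 80% concordance:

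- Treating events as independent: 1.96 × √(0.8 × 0.2 / 500) = 3.5 points
- m = 1, CV = 0: DE = 1, half-width 3.5 points
- m = 5, CV = 2, ICC = 0.5: DE = 1 + (25 − 1) × 0.5 = 13, half-width 3.5 × √13 = 12.6 points

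For the counts in step 2, Σn² ≈ 95 × 1.5² + 5 × 30² = 4,714 and Σn²/Σn = 16.1. Effective independent events = 292.5 / (1 + 15.1 × ICC), which is about 116 at ICC 0.1, 53 at 0.3, 34 at 0.5 and 18 at 1.

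**6. No matching rule.** With 100 record events, 60 matched device events plus 40 false ones give (60 + 40) / 100 = 100%. With 80 false ones, the rate is 140%.

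**The case against.** The strongest reply is that pooling is an inference. Section 5.2 gives a ratio and does not say it is summed over subjects. A ratio per subject, summarised by mean and standard deviation, is not excluded, and neither is one event per type per subject. Under that count the gap disappears in a rate given by type, and in a rate over all five types no subject could add more than five events. This stands in part: the supportable defect is an undefined event and unit, not a deliberate choice of weights. The plain reading remains an event-level ratio, and nothing in the plan prevents the problem.

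Three further points stand. The large gap in step 2 needs both 30 events per subject and much worse detection in those same subjects. The figure of 18 effective events needs complete within-subject correlation. No interval or test is planned, so no error rate is at risk. Even so, a descriptive rate must be interpretable, and section 1.4 intends the results to inform policy.

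A reader might infer more than the documents support:

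- **That a handful of subjects could set the result of the whole study.** No primary endpoint is named, and the maximum and minimum differences are not weighted by repeated events. They do not replace event detection, however, since they have no arrhythmia measure and name only the watch.
- **That subjects without a record event have no influence.** As written, their device events still enter the numerator.
- **That a per-subject measure should replace the event-level rate.** Event-level detection is a legitimate target for monitoring. Scoring a subject as a success when at least one event is detected would count 1 of 30 as full success. In step 2, with independent misses and the other 95 split evenly between one and two events, it would read about 97.5% and hide the five poor performers.

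**Conclusion.** The concern holds for the concordance rate only, and conditionally. If repeats within a subject are counted, subjects with many events can dominate the rate, and the event total does not show its precision. The size cannot be computed from the documents. Under the assumptions shown, the gap from the per-subject mean is 0 to about 40 points, and the 95% half-width for 500 events at 80% is 3.5 to 12.6 points. The gap is zero for a by-type rate if each subject adds at most one event per type, and also if detection is unrelated to event count. The harm is to interpretation and precision, not to type I error. The documents support adding measures beside the event-level rate, not demoting it. This is a cheap improvement.

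**What to change.** In section 5.2:

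1. Define an event by its start, its end and the time window for matching, and state whether repeats in a subject count.
2. Count in the numerator only device events matched to a record event.
3. Report the rate by event type and by device, with 95% intervals from resampling whole subjects.
4. Beside that rate, not in place of it, report the mean of the per-subject proportions of record events detected, the percentage of subjects with no record event in whom the device recorded one, and the largest share of events from any one subject.

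The cost is SAP wording and modest analysis of data already to be collected. The downside is wider, more honest intervals and two summaries that may differ and need explaining. Where few subjects have a given event type, the interval will itself be unstable, so the number of contributing subjects should be printed beside each rate.

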3.1 General Design

We will perform a prospective, non-blinded, exploratory study to assess the accuracy and safety of smart technology in the endoscopy suite for patients undergoing gastrointestinal endoscopic procedures with sedation. We will also simultaneously perform an assessment of patient and provider preferences using narrative-driven, qualitative evaluation.

Patients will be identified by reviewing daily procedure listings on endoscopy units on Alfred 6, Gonda 2 and Gonda 9. Recruitment will occur over the phone the day prior to a procedure, or the pre-procedure areas on the day of the procedure. Patients who meet inclusion criteria and consent to participation in the study will be provided the smart devices. The devices will be secured to the wrist and torso by study personnel prior to administration of sedatives. The smart watch will be programmed to record respiratory rate, heart rate, and oximetry using native, first party device applications. These applications include *Blood Oxygen* (measures oxygen saturation), *ECG* (records single lead ECG), *Heart Rate* (heart rate), and *Health* (which logs respiratory rate while sleeping). The QardioCore ECG device will measure a single-lead ECG, heart rate, skin temperature, and respiratory rate.

The patient will undergo his or her scheduled procedure. Patients, proceduralists and anesthetists will not be blinded to their enrollment as the devices will be visible. On completion of the procedure, the devices will be removed by the study coordinator and data downloaded onto a central device for analysis. Procedural information will be extracted from the operative note, sedation record, and anesthesia encounter in EPIC. The day after the patient's procedure, a survey will be submitted to them electronically which will remain open until 14 days after

the procedure. Aen electronic reminder will be sent if uncompleted at 7 days, followed by a telephone reminder if not completed at 13 days. There will be no additional patient follow up after completion of the survey. At study completion, a survey will be sent to involved proceduralists and anesthetists.

3.2

Figure 1: Study Design

[figure not shown]

Table 1. Schedule of Events

	Baseline Screening & Enrollment Visit 1 Days -60 to 0	Accrual: Study Intervention Visit 2 Day 0	Patient Survey Visit 3 Day +1 to +14	Provider survey Days 0 to 180
Inclusion/ Exclusion	X	X (if not performed earlier)		
Device(s) Placement/ Recording		X		
Patient Survey			X	

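### Section 5.2 divides a wearable event count by a record event count without a counting unit, sampling interval or common time base, so if the sources sample at different rates the concordance rate reflects sampling density as well as detection.

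*Combined protocol and SAP*

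**What the plan says.** Section 5.2 (Statistical Methods) defines the rate of concordance as the number "of events recorded on wearable device / events noted on anesthesia record". The qualifying events are listed as "Events to be recorded include tachycardia (HR > 100), bradycardia (HR < 60), desaturation" (saturation below 88%), followed by "any arrhythmia, and tachypnea (RR > 18". The four vital-sign events are bare cut-offs and arrhythmia has no criterion. Neither section 5.2 nor any other section gives a minimum duration, a rule for when one event ends and the next begins, a counting unit, or a way of aligning the two sources in time.

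Section 3.1 (General Design) describes the sources. On the wearable side, "The smart watch will be programmed to record respiratory rate, heart rate, and oximetry using native, first party device applications". Respiratory rate comes from an application "which logs respiratory rate while sleeping". A second device overlaps with the watch: "The QardioCore ECG device will measure a single-lead ECG, heart rate, skin temperature, and respiratory rate". On the reference side, "Procedural information will be extracted from the operative note, sedation record, and anesthesia encounter in EPIC". No sampling or charting interval is given for either side.

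Section 5.2 also plans a second comparison, the difference in maximum and minimum heart rate, respiratory rate and saturation between watch and sedation record.

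**The concern.** A ratio of two counts measures detection only if both counts use the same unit and both sources had the same opportunity to register an event. Here the unit is open and the opportunity is probably unequal: automated application logs on one side, entries in a chart on the other. A heart rate drifting between 58 and 62 for ten minutes may be many bradycardia events on a source read every few seconds and one or two in a chart.

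The primary objective in section 2.1 is to measure accuracy, and this ratio is the only event-level measure of it. If it moves with sampling density, a value above 1 may be taken for over-detection, or a value below 1 for missed events, when the device made no error. An analyst who fills the gap with a sensible counting rule is still exposed, because the choice of rule does not equalise the sampling.

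**Working it through.** **Plan's own figure.** There is none to reproduce. The documents give no expected concordance, event count or sampling interval, and section 5.1 says no power analysis was done. The only number taken from the plan besides the cut-offs is the enrolment of 500 (section 4).

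**Step 1: one episode.** A 10-minute (600 s) tachycardia read every d seconds gives 600/d readings above the cut-off: 120 at 5 s, 10 at 60 s, 2 at 300 s, 1 at 600 s. Against a 5-minute record, an error-free wearable counted by readings scores 120/2 = 60, 10/2 = 5 or 1/2 = 0.5. Counted as one episode on each source, it scores 1/1 = 1.

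**Step 2: error-free wearable, mixed population.** Both sources read the same true heart rate and differ only in interval. Assumptions, none from the documents except the 500:
- 500 patients, 30 minutes each
- patient mean heart rate normal with mean 75 and SD 12
- within-patient SD 6, first-order autoregression with coefficient exp(-5/tau) per 5 s step, correlation time tau of 60, 180 or 600 s
- events: heart rate above 100 or below 60

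Ratio = count at the wearable's interval / count at the record's interval. At tau = 180 s:

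| Counting unit | 5 s vs 5 min | 60 s vs 5 min | 10 min vs 5 min | 5 min vs 60 s |
|---|---|---|---|---|
| Reading | 30,698/504 = 60.91 | 2,558/504 = 5.08 | 253/504 = 0.50 | 504/2,558 = 0.20 |
| New crossing | 2,231/244 = 9.14 | 646/244 = 2.65 | 163/244 = 0.67 | 244/646 = 0.38 |
| Ever/never per patient and type | 298/183 = 1.63 | 258/183 = 1.41 | 148/183 = 0.81 | 183/258 = 0.71 |

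Over all three correlation times, against a 5-minute record:
- crossings: 7.1 to 14.4 (5 s), 2.1 to 3.5 (60 s), 0.57 to 0.67 (10 min)
- per patient: 1.41 to 2.15 (5 s), 1.29 to 1.59 (60 s), 0.74 to 0.81 (10 min)

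With the wearable at 5 min and the record at 60 s, crossings give 0.28 to 0.47 and per-patient counts 0.63 to 0.77.

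**Step 3: heart rate nearer the bradycardia cut-off.** Same kind of process, 30 minutes, entries below 60, mean entries per subject:

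| Mean, SD, tau | 5 s | 60 s | 5 min | 5 s / 5 min | 60 s / 5 min |
|---|---|---|---|---|---|
| 62, 4, 60 s | 20.7 | 5.1 | 1.4 | 14.8 | 3.6 |
| 62, 4, 180 s | 12.0 | 3.4 | 1.2 | 10.0 | 2.8 |
| 66, 5, 120 s | 8.1 | 2.1 | 0.63 | 12.9 | 3.3 |
| 70, 6, 120 s | 3.95 | 0.97 | 0.26 | 15.2 | 3.7 |

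Repeat runs, one of them with a different convention for the last chart point, gave 8.4 to 15.8 (5 s) and 2.4 to 3.8 (60 s). Counting patients with any event gave 1.1 to 3.5.

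**Step 4: does a common grid cure it?** With both sources reduced to the same 5-minute time points and one rule, the step 2 ratio is exactly 1.00 under all three counting units (for readings at tau = 180 s, 504/504). A finer grid does not work. With a 5-minute record carried forward onto a 1-minute grid, gaps under 5 minutes merged and a minimum duration of 1, 2 or 3 minutes, the error-free ratio in the step 3 scenarios ran from 0.31 to 3.1. A grid cannot recover values the coarser source never held.

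**Step 5: overlapping types.** An irregular rhythm at rate 120 meets both the tachycardia and the arrhythmia definitions. Coded twice on both sources it contributes 2/2 = 1. Coded twice on the wearable and once in the record it contributes 2/1 = 2.

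**The case against.** The strongest reply is that several stronger readings go beyond the text, and this is right.

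- A reader might infer that the plan defines an event as any crossing of a cut-off. It does not. It leaves the unit open, and an event noted on the record could well mean a clinician-documented episode, or one event per patient and type.
- A reader might infer that an error-free wearable must give a wrong rate. That holds only if the sources are sampled at different rates, and no interval is documented. With equal sampling on aligned time points the ratio is 1.00. Nor is the error always inflation: a denser record pushes the ratio below 1.
- A reader might infer that overlapping types bias the ratio in themselves. They do not if both sources are coded alike, and 5.2 does not say that types are pooled.
- A reader might infer that the primary objective cannot be answered. Section 5.2 also plans maximum and minimum differences, which need no event definition, so accuracy does not rest on this ratio alone. Those extremes do depend on sampling density too.

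The large ratios at 5 s also owe much to a noise process that re-crosses a threshold often, and the documents name no 5 s data stream.

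What remains is the core point. That the study is exploratory and involves no testing (sections 3.1 and 5.1) does not help, because the problem is in the estimate itself. The mildest reading, ever/never per patient, still departs from 1.00 when sampling is unequal.

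**Conclusion.** The concern holds in conditional form. Section 5.2 leaves the counting unit, episode rule, sampling intervals and time base unspecified. If the two sources sample at different rates, the concordance rate reflects sampling density as well as detection. Under the assumed intervals (wearable at 5 s or 1 min, record at 5 min), an error-free wearable scores about 3 to 15 counting crossings when heart rate lies near the cut-off, 2.1 to 14.4 in the mixed population, and about 1.1 to 3.5 per patient. With the record denser than the wearable it scored 0.20 to 0.81, depending on the intervals and the counting unit.

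These sizes rest on assumed intervals, procedure length and heart-rate behaviour, and only heart-rate events were simulated. That a bias exists under unequal sampling, and that its direction depends on which source is denser, does not rest on the particular values chosen. Unequal sampling is likely from section 3.1 but not documented.

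**What to change.** Add to section 5.2, before data are analysed:

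1. Record the actual sampling interval of each source for each signal, and name the wearable that supplies the numerator for each signal, since heart rate and respiratory rate come from both.
2. For each signal, reduce both sources to a common, clock-aligned time grid no finer than the coarser source. Use only grid points where both have a value, so that respiratory rate not logged outside sleep is not read as absence of tachypnea.
3. Apply one identical rule to both sources: an episode is a run of consecutive grid points beyond the cut-off. State one arrhythmia criterion and use it for both. The listed cut-offs need not change for this purpose.
4. Report concordance separately by event type, so that a fast or slow arrhythmia is not counted twice in one total.
5. Compute the any-event-per-subject (yes/no) version on the same grid. On unequal sampling it is distorted as well.

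The cost is a short paragraph, a record of intervals and clock offsets, and some programming. The loss is that excursions shorter than the coarser interval are not counted. They can be listed descriptively by source. The grid also gives the countable units that any later event-by-event matching would need.

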Statistical Methodology	All continuous variables will be expressed as mean and standard deviation. Categorical variables will be expressed as percentages.

1 Introduction

This document is a clinical research protocol relating to a prospective study of the role and accuracy of consumer-facing wearable technology in gastrointestinal endoscopy. The described study will be conducted in compliance with this protocol, applicable United States government regulations and Mayo Clinic policies and procedures.

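### The pooled maximum and minimum SpO2 differences say little about accuracy at low saturation; make the maximum descriptive and report the minimum separately below and at or above 88%

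*Combined protocol and SAP*

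**What the plan says.** The primary objective (Section 2.1) is accuracy against the equipment now in use. Section 5.2 gives two kinds of accuracy result.

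- **Event concordance.** Several events are listed, among them "desaturation (peripheral O₂ saturation < 88"%). The rate is defined as the number "of events recorded on wearable device / events noted on anesthesia record". Matching by time or by event is not stated.
- **Differences in extremes.** The plan adds: "We will also calculate the difference in maximum and minimum heart rate, respiratory rate, and oxygen saturation recorded by the watch compared to the sedation" (the sedation record).

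For summaries, the Study Summary says "All continuous variables will be expressed as mean and standard deviation", and Section 5.2 repeats the rule. The plan sets no breakdown by reference SpO2, no limits of agreement and no acceptance limit. It does not say whether the differences are signed or absolute.

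Section 4 expects to "enroll 500 subjects to the study", and eligibility (Section 4.1) does not select for desaturation risk. Section 5.1 says: "Power analysis not performed as this study is descriptive and we do not plan to perform any statistical testing". The documents give no SpO2 distribution and no expected desaturation rate.

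**The concern.** Two features of SpO2 limit what these summaries can show.

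First, the scale stops at 100%. If most subjects reach or approach 100% at some point, both instruments have a maximum in a narrow band, and their difference is small whether or not the watch follows the patient. The maximum also says nothing about low values, and a low value is the plan's own SpO2 event.

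Second, the difference in minima is averaged over everyone. Subjects who never desaturate contribute small differences, and these dilute a large error confined to those who do.

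The study is descriptive, so its summary tables are its result. A small pooled mean could be read as accuracy at low saturation, which it does not measure. Sampling both sources at the same times would not cure this.

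**Working it through.** The plan states no SpO2 figure, so there is nothing of its own to reproduce. From the documents: N = 500 enrolled, the 88% limit, mean and SD as summaries. Assumed: the share p of subjects with reference SpO2 below 88% (2% to 30%); the amount d by which a watch that misses desaturations overstates their minimum (8 to 15 points); the SD s of ordinary error (1.5 or 3 points, no bias in other subjects). Differences are taken as signed, watch minus record.

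**1. Minimum SpO2, pooled mean.** Mean difference = p × d.

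| p | d = 8 | d = 10 | d = 15 |
|---|---|---|---|
| 2% | 0.16 | 0.20 | 0.30 |
| 5% | 0.40 | 0.50 | 0.75 |
| 10% | 0.80 | 1.00 | 1.50 |
| 20% | 1.60 | 2.00 | 3.00 |
| 30% | 2.40 | 3.00 | 4.50 |

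The mean stays at or below 1 point only if p ≤ 1/d: 12.5%, 10% or 6.7% for d = 8, 10 or 15. Among the desaturating subjects alone it is d.

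**2. Minimum SpO2, pooled SD.** SD = √(p(1 − p)d² + s²). At p = 5%, d = 10:
- s = 1.5: √(4.75 + 2.25) = 2.65, against 1.5 without misses.
- s = 3: √(4.75 + 9) = 3.71, against 3.0 without misses.

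The SD does rise. But take watch A with s = 1.5 that misses every desaturation (mean 0.50, SD 2.65), and watch B with a uniform bias of 0.50 and noise SD 2.65 at every saturation. Their pooled summaries are identical. Below 88%, A is wrong by 10 points on average and B by 0.5.

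**3. Dependence on the kind of failure.** Simulation with p = 5% to 20%, and other subjects' minima averaging 93 to 96:

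| Watch | Pooled mean | Mean in desaturating subjects |
|---|---|---|
| Cannot read below 90 | 0.3 to 1.5 | 6.8 |
| Minima unrelated to truth, spread like normal subjects | 0.5 to 2.5 | 9.3 to 12.2 |
| Always reads about 97 | 1.6 to 5.8 | 13.2 to 13.3 |

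**4. Maximum SpO2.** Let each instrument independently show a maximum of 100% with probability h, and otherwise 97, 98 or 99 with equal chance. The two readings are then unrelated. The mean difference is 0. The share within 1 point is h² + 2h(1 − h)/3 + (1 − h)² × 7/9.
- h = 0.5: 0.250 + 0.167 + 0.194 = 61%, SD 1.6.
- h = 0.9: 0.810 + 0.060 + 0.008 = 88%, SD 0.9.

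**5. Both measures together.** A second simulation used seven same-time readings per source, usual SpO2 about 98.5% (within- and between-subject SD 0.8, capped at 100), and one dip to 80–87% in 5% or 15% of subjects. A watch unrelated to the patient gives a mean maximum difference of 0.0, with 86% within 1 point. Its pooled minimum difference is 0.7 or 2.1 points, against 13.9 in those who dip. The SD of that difference is about 1.4 without dips, 3.4 at 5% and 5.2 at 15%.

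**6. The concordance ratio.** At N = 500, p = 5% and one event per subject, there are 500 × 0.05 = 25 reference events. A watch that never reads below 88% scores 0/25. A watch with 25 false low readings in other subjects and no true detection scores 25/25, because matching is not required.

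**The case against.** The strongest reply is that the plan already looks for this failure. The desaturation event comes just before the max/min differences in Section 5.2, and a watch that never reads low would score zero on it. The SD is reported too, and 0.7 with an SD of 3.4 does not look like close agreement. A merely noisy watch is also caught: with 3-point error its maximum difference in the second simulation is only 0.5, but its minimum difference is about −3.0 at 5% dips. The study is exploratory, and no decision rule rests on these means.

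Most of this stands. A reader might infer that a watch blind to desaturation would pass through the plan with near-zero differences. The documents do not support that. The concordance ratio would expose it, and a small pooled minimum difference needs a low desaturation rate that the documents do not give. At p = 20% the mean is already 1.6 to 3.0 points, and a watch fixed near 97 shows 1.6 points or more even at 5%. Nor does the argument carry over to heart rate or respiratory rate: the 100% ceiling is specific to SpO2, and no calculation here supports splitting those two.

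What the reply does not answer: the ratio is of unmatched counts and gives no size of error; the SD has no benchmark and cannot say where the error lies; and neither makes the maximum-SpO2 difference informative.

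**Conclusion.** The point holds as a limit on interpretation and an inexpensive improvement. It is not a flaw that conceals device failure.

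If most subjects read near 100% on both instruments, the difference in maximum SpO2 says little about accuracy. It could still show a marked downward bias. The pooled mean difference in minimum SpO2 shrinks an error of 8 to 15 points to about 0.2 to 1.5 points when 2% to 10% of subjects desaturate, and shrinks it less at higher rates. The desaturation rate, the size of the miss and the clustering near 100% are all assumptions. That a pooled mean dilutes an error confined to a subgroup is arithmetic and does not depend on them. The planned ratio and SD give partial protection, but no planned result shows the size of the error at low saturation.

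**What to change.** In Section 5.2:

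1. State that maximum SpO2 is reported as description only and not as an accuracy measure.
2. Report the minimum-SpO2 difference (mean, SD and number of subjects) separately for subjects whose reference minimum is below 88% and for those at or above 88%. This is the plan's own event limit.
3. Place this table next to the planned desaturation concordance, so that detection and size of error are read together.

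The cost is a few words and one table from data already collected. The downside is a small low group: 500 × 0.02 = 10, 500 × 0.05 = 25 or 500 × 0.10 = 50 subjects at assumed rates of 2%, 5% or 10%, and fewer if some leave the final analysis for incomplete data. Its count should therefore always be shown. Even so, with a within-group SD of 3 points (assumed; larger if the depth of dips varies), the standard error of the mean would be 3/√10 = 0.95, 3/√25 = 0.60 or 3/√50 = 0.42 points. An error of 8 points or more would be plain.
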